Male and female veterans of all ethnicities will be sought to participate. All participants must meet the following criteria during intake or analysis: 1) be between 18 and 64 years of age; 2) meet DSM-5 criteria for current Post Traumatic Stress Disorder, as assessed by study staff using the Clinician Administered PTSD Scale-5 (CAPS-5); 3) be fluent in English; 4) have vision corrected to be able to see a computer display clearly; 5) be able to provide informed consent and be able to follow verbal or written instructions; 6) assessed as not a significant harm to self or others.

SUBJECT EXCLUSION CRITERIA

All participants admitted to the unit will be allowed to partake in the study. Those with contraindications to the fMRI will complete behavioral only tasks. The following exclusion criteria will be applied to all participants during analysis: younger than 18 or older than 65; self-reported PTSD symptoms for less than six months; diagnosed seizure disorder; history of stroke; Cushing's syndrome; history of moderate to severe traumatic brain injury (TBI); electroconvulsive therapy within 5 years; history of chemotherapy for cancer; contraindications to fMRI; current pregnancy; diagnoses of schizophrenia, schizoaffective disorder, delusional disorder, organic psychosis, bipolar disorder, or depressive disorder with psychosis as assessed with SCID-5-RV (and not stabilized or in remission); symptoms meeting criteria for a substance use disorder within the previous 30 days (assessed through SCID-5, Alcohol Use Disorders Identification Test score > 8); meets criteria for acute psychiatric or medical admission; assessed as significant risk of harm to self or others; use of non-prescribed narcotics; acute cardiac difficulties (unless cleared by a cardiologist); psychotic disorders not otherwise specified assessed with SCID-5-RV; subjects using benzodiazepines (they will be given the opportunity to discontinue and must be off for at least two weeks prior to the beginning of the study); psychotropic medications must be stabilized for at least two weeks prior to the beginning of the study and remain stabilized throughout the entire duration of the study; if changed, the subject may be dropped from the study at the discretion of the research staff; positive drug tests during the course of the study will be grounds for disenrollment from the study. Given the high prevalence of psychotropic medication usage in

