Written informed consent will be obtained after the veteran is admitted to the Salem VA residential PTSD unit. Upon arriving at the Salem VA PTSD residential unit, individuals will again be given an overview of the study, including a basic description of the study design, and any questions they have will be answered. As part of the intake process within the unit, a variety of clinician-administered and self-report measures are completed to evaluate psychiatric symptoms and current psychosocial functioning, including the PTSD Checklist (PCL-5); Beck Depression Inventory (BDI-II); Posttraumatic Cognitions Inventory (PTCI); five facets of mindfulness; Insomnia Severity Index (ISI); Acceptance and Action Questionnaire (AAQ-2); and Disturbing Dreams and Nightmare Severity Index (DDNSI), etc (see attached for samples). S/he will be asked to consent to the use of the audio recordings of his/her clinical interviews during the research intake screening (SCID-5-RV & CAPS-5), and of his/her individual therapy sessions, so that the reliability of assessment procedures and treatment fidelity can be evaluated. In addition, s/he will be asked to give permission for research staff to access intake assessment information and medical record history, in order to further evaluate eligibility criteria for the study.

Interested veterans will also be asked to complete a pre-consent MRI screening form (attached) over the telephone during their initial phone screen with study staff. If contraindications to MRI involving potential metal are identified (e.g. shrapnel, medical devices, etc.), veterans will be instructed to request a written note from their medical provider stating that any metal in their body is MRI safe. A radiologist from Salem VAMC may evaluate the safety of the veteran to participate in the study, should he or she desire to participate. If a participant is ineligible to participate in the MRI portion of this study, they may participate in the rest of the study and complete the tasks outside of the scanner.

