Additionally, Drs. [name] or [name] will be alerted immediately and study staff will brief the veteran's VA clinician. If the Veteran has experienced distress but is stable, study staff will notify the patient's VA clinician immediately by telephone or pager. If the veteran must be transported via ambulance, study staff will notify the VA ED, nursing staff on the residential unit, and the Veteran's VA clinician. If the veteran has expressed homicidal ideation or intent to harm others, security staff will be notified.

For an Information Security or Privacy incidents, suspected or actual, the ACOS for Research, Privacy Officer and Information Security Officer are notified within 1 hour of discovery.

CONSENT PROCEDURES:

If individuals entering the PTSD residential unit are potentially eligible to participate, based on the phone screen and review of intake assessments, the research project will be explained, and any questions that potential participants have will be answered by study staff. Individuals expressing interest in participating will be asked to complete a pre-consent MRI screening questionnaire that evaluates contraindications to magnetic resonance imaging. For those who completed the MRI screen over the phone with study staff, they will be asked to review their MRI screening form and update if needed. If there are any concerns about a veteran's safety for MRI procedures, the veteran may be asked to complete X-rays to ensure the absence of metal. Veterans will be informed there is no charge for any X-rays and will be reminded that they may decline to participate in the study at any time. A radiologist at Salem VAMC will review the veteran's chart and x-rays and will make the final determination concerning the safety of the subject's participation in the fMRI for research purposes.

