Individuals who remain eligible for the study following intake assessments, review of medical record and assessment for contraindications to MRI will be provided with a study consent form to review. Subjects will be given a quiet place and ample time to review this form independently. A study staff member will also review the contents of the consent form with each potential participant and answer any questions the participant may have prior to providing consent. The study staff will be sensitive to cultural, educational, or language difficulties and will ensure that the subject adequately understands the procedures, benefits, and risks of the study and has the capacity to provide informed consent prior to proceeding with the study. Informed consent will be obtained in writing on the study's consent form that will be stored in a secure locked cabinet for the duration of the study. The subject also will be provided with a copy of the consent form.

If participants are ineligible for participation based on their screening information or choose not to participate in the study, initial screening information linked to subject identity will be destroyed upon completion of the study. The initial screening information will be kept until completion of the study to ensure that the same person is not screened for participation more than once. Study staff will emphasize to all participants that they may withdraw from the study at any time with no adverse consequences and will be compensated for their participation in the study up to that point.

In response to COVID-19, participants who have been accepted into the PTSD unit and passed the initial phone screen will be mailed informed consent and HIPAA forms via FedEx, USPS or UPS. Study staff will follow up with the interested Veteran via phone or VA Video Connect to (1) confirm they have received and read the ICF and HIPAA form, (2) answer any questions the Veteran may have, (3) provide instructions for filling out the forms, and (4) have the Veteran complete and sign the forms while on the phone. The Veteran will then be instructed to mail the forms back to study staff using the provided envelope and label with tracking.

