After study staff have received the signed ICF and HIPAA forms, they will contact the Veteran via telephone or VA Video Connect to conduct the pretreatment interviews (SCID and CAPS) to establish final study eligibility. No study procedures will be conducted prior to receiving signed informed consent and HIPAA forms. Interviews will be scheduled as close to estimated admission as possible. Should the time elapsed between the interviews and admission surpass 2 months due to delayed admission, interviews will be readministered to ensure data validity.

For eligible Veterans who are enrolled, informed consent will be reviewed and confirmed via the established in-person procedure after admission to the PTSD unit. This will occur when normal research and clinical procedures are restored.

Veterans who have been accepted to the PTSD unit and have passed the initial study phone screen may be invited to complete the informed consent process in-person if they are staying locally prior to being admitted to the unit. Once informed consent has been obtained, study procedures such as the pretreatment interviews, questionnaires and/or scans may also be completed. Study procedures will be conducted during the week prior to the Veteran's planned admission date. If a Veteran subsequently defers or declines admission to the PTSD residential program, they will be unenrolled from the study, but may participate at a future date. No study procedures will be conducted prior to obtaining informed consent.

Similarly, Veterans may be invited to complete posttreatment interviews, questionnaires and/or scans if they are staying locally after discharging from the PTSD unit. Study procedures will be conducted as close to discharge as possible and not past the week following discharge.

In some cases, Veterans may be offered travel and/or accommodation resources if they wish to complete study procedures in-person prior to their admission and/or after discharge from the unit. No study procedures will be conducted prior to obtaining informed consent. These resources will be funded by the National Institutes of Health under Award Number UL1TR003015. Funds from this award will be managed and distributed by the integrated Translational Health Research Institute of Virginia (iThriv), which is a NIH funded program hub that aims to accelerate health

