discoveries and improve health outcomes for all people. Funds will be used directly to pay for these offered resources i.e. the funds will not be distributed to the study staff or to the Veterans.

Veterans wishing to use these resources will be asked initially for their verbal consent to releasing their name and phone number to the iThriv partnership manager for the purposes of booking their travel or accommodations. Upon arrival to their in-person research session, they will be asked to sign the VA Form 10-5345 (Request for and Authorization to Release Medical Records or Health Information). Demographic information such as race, sex, ethnicity and race will also be requested to be released to the iThriv program for NIH grant reporting purposes.

COST/COMPENSATION:

During the course of this study, no medical procedures will be performed and no insurance companies will be billed. All expenses incurred in performing the study will be paid for by the VAMC. Subjects will be compensated for their participation in the fMRI visits of the study; for the transportation time between the Salem VAMC and the FBRI to complete the fMRI visits; and for the 3 and 6-month follow-up assessment sessions. Subjects will be paid after each assessment portion of the study protocol (i.e., pre-treatment, post-treatment, 1-week, 3-months, and 6-months follow ups) via either direct deposit or check mailed from VA Financial Services. They will be informed that if they withdraw from the study at any time, they are still entitled to the compensation they have earned through that point in the study.

Assessment/questionnaire compensation:

For assessments and questionnaires that are not included in VA standard practice of care, such as CAPS-5, SCID-5, AQ, etc., the participants will be compensated according to a structured payment plan for completing each assessment session. See payment structure below in Table 1. Payment is based on the modal time required to complete each portion of the procedures at a rate of \$15/hr. Some or all of these assessments will be completed over the phone one week after leaving the unit, and at 3-month and 6-month follow-up phone assessment sessions.

Task compensation:

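### On the standard in-person route, X-rays and radiologist chart review done to clear a veteran for the research fMRI come before written consent

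*Protocol*

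**What the plan says.** All references are to the protocol; the SAP is silent on this point.

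- CONSENT PROCEDURES, standard in-person route: the project is explained and interested veterans are "asked to complete a pre-consent MRI screening questionnaire that evaluates contraindications to magnetic resonance imaging". If a safety concern arises, "the veteran may be asked to complete X-rays to ensure the absence of metal", at no charge and with a reminder that they may decline. A radiologist then reviews chart and films and decides on "participation in the fMRI for research purposes".
- The next paragraph of the same section: those still eligible after intake assessments, record review and "assessment for contraindications to MRI will be provided with a study consent form". At that point staff go through the form, check understanding and capacity, and obtain consent in writing.
- Initial Visit: Consent and Pretreatment Procedures: study procedures begin once written consent has been obtained.
- CONSENT PROCEDURES, later paragraphs on veterans staying locally and on travel support: "No study procedures will be conducted prior to obtaining informed consent". The COVID-19 paragraphs carry an equivalent rule tied to receipt of the signed consent and HIPAA forms.
- I. Recruitment: written consent is obtained after admission, and in the same paragraph "s/he will be asked to give permission for research staff to access intake assessment information and medical record history", so that eligibility can be evaluated further. MRI-ineligible veterans may take part and do the tasks outside the scanner.
- RISKS & BENEFITS: after a positive MRI screen, the possible need for an X-ray is explained, the veteran may stop, and the radiologist looks at existing records and requests films if needed.

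**The concern.** The X-ray has one stated purpose: to clear the veteran for a research scan. No clinical use is given. A site that follows CONSENT PROCEDURES in the order written would carry it out before the person has seen the consent form and before anyone has documented that he or she understands the study and can consent. The protocol itself says that people with mental illness can be a vulnerable population and promises particular care over consent. The same order puts research review of the medical record ahead of the form, although Recruitment treats access to the record as something the veteran is asked to permit.

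What is at stake is participant protection and a procedure that staff can follow. No estimand, bias or power question turns on it.

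**Working it through.** The point concerns the order of steps, so the check is to set the sections side by side.

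1. **Order on the in-person route.** CONSENT PROCEDURES runs: explanation, MRI questionnaire, X-ray if there is concern, radiologist review of chart and films, then the consent form for those still eligible. The form is conditional on the MRI assessment having been made, so the X-ray that informs that assessment comes first.
2. **The rule.** The Initial Visit section gives the general order: written consent, then study procedures. The explicit prohibitions later in CONSENT PROCEDURES repeat it for the COVID-19, local-stay and travel-support routes. The general rule is the one that bears on the in-person route.
3. **Is the X-ray a study procedure?** The term is not defined. The MRI questionnaire is openly labelled as preceding consent; the X-ray carries no such label and no separate authorisation. Its only stated use is clearance for the research scan.
4. **Safeguards before the X-ray.** There is an explanation, a statement that there is no charge, and a reminder of the right to decline. Written consent and the check of understanding and capacity come later.
5. **Does RISKS & BENEFITS settle the timing?** It describes the X-ray step in words that could fit someone already taking part, such as ending participation or carrying on with the study. That is compatible with an X-ray after enrolment but does not say so, and it does not match step 1.
6. **Medical record.** Recruitment has the veteran asked for permission; CONSENT PROCEDURES places record review before the form. Neither says when the permission is given relative to the review.
7. **Is clearance needed before consent?** SUBJECT EXCLUSION CRITERIA, Recruitment and the task description all allow MRI-ineligible veterans to do the tasks outside the scanner. Enrolment therefore need not wait for clearance.
8. **Cost in enrolment terms.** SAMPLE SIZE takes 44 completers in each of two groups, so 2 × 44 = 88, and 88 × 1.5 = 132. The allowance is 132 − 88 = 44 places, covering both those who fail criteria and those who do not finish. Contraindications to fMRI stand in the list introduced by "The following exclusion criteria will be applied to all participants during analysis". A consented veteran who proves MRI-ineligible and is excluded on that ground uses one of the 44.

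**The case against.** The best defence is that clearance X-rays are screening rather than study procedures. The local-stay paragraph illustrates study procedures by interviews, questionnaires and scans, and the protocol openly places some MRI screening before consent. The veteran is told about the study and may refuse, and RISKS & BENEFITS can be read as placing the X-ray after enrolment. X-rays are also occasional: Recruitment first asks for a provider's note, and the radiologist looks at existing records before requesting films. All of this stands as description. It narrows the point to an occasional X-ray without written consent. It does not remove the conflict, because nothing in the protocol exempts the X-ray from the consent-first rule and the capacity check still comes later.

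Several stronger readings are tempting and are not supported:

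- **That veterans are X-rayed with no consent of any kind.** An explanation and an opportunity to decline come first; what is missing is written consent.
- **That records are opened without permission.** Recruitment provides for permission. The defect is that its timing is not settled. The consent form is not among the documents, so what it authorises cannot be checked.
- **That pregnancy is not considered until analysis.** It is on the list applied at analysis, but STUDY DESIGN invites to the imaging battery those who meet the criteria, and fMRI contraindications, on the same list, are plainly checked beforehand.
- **That the COST/COMPENSATION statement that "no medical procedures will be performed and no insurance companies will be billed" contradicts the X-ray provision.** It is a sentence about billing, loosely worded, and says nothing about consent.
- **That a count can be had by applying an assumed positive-screen rate to 132.** No rate is given, 132 counts enrolled rather than screened veterans, and a positive screen need not lead to an X-ray.

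**Conclusion.** The point holds in this form: as written, the standard in-person route allows a research-only X-ray and radiologist chart review before written consent, contrary to the Initial Visit rule and ahead of the check of understanding and capacity. It affects only veterans whose MRI screening raises a concern and, of those, only the ones for whom chart review or films are requested. Their number is unknown. Separately, Recruitment and CONSENT PROCEDURES do not agree on when permission for research review of the record is obtained.

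The conclusion rests on reading CONSENT PROCEDURES as a sequence, which its conditional wording supports, and on treating an X-ray whose only stated use is research clearance as covered by the consent-first rule. If the site in fact obtains consent first, the text should still be changed to say so. The change should be made because it protects participants at little cost; it does not affect the validity of the treatment comparison.

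**What to change.** Reorder the in-person part of CONSENT PROCEDURES so that the signed consent form and HIPAA authorisation come before any research-only X-ray, radiologist chart review or research review of the medical record. Leave the MRI questionnaire as the only MRI screening step before consent. State whether clearance X-rays and record review count as study procedures. Bring Recruitment, Initial Visit, the COVID-19, local-stay and travel paragraphs, and the MRI-screen paragraph of RISKS & BENEFITS into line, and mention the X-ray among the risks, where it now appears only as a clearance step.

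Cost: protocol and consent-form wording, with no new procedure or staff. The real downside is that some consented veterans will prove MRI-ineligible. They can do the tasks outside the scanner, but as SUBJECT EXCLUSION CRITERIA stands they may be dropped at analysis and so draw on the 44-place allowance. The sponsor should say whether they count towards the 88, so that this cost is known.

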JUNE 1, 2023

EFFICACY AND NEURAL MEDIATORS OF
RESPONSE TO TRAUMA MANAGEMENT
THERAPY FOR PTSD
NCT03449576

Analysis of primary clinical outcome hypothesis for D2354-R “Efficacy and Neural Mediators of Response to Trauma Management Therapy for PTSD”

A regression approach was used to test the effect of treatment type (TMT, EXP+EDU) on both primary (CAPS-5 and SAS-SR) and secondary (PCL-5, AQ, ITS) outcome measures across Time (pre-treatment, post-treatment). The Time x Treatment interaction was be used to test whether TMT improves outcomes relative to EXP+EDU, and age was entered as a co-variate as the two treatment arms differed in age at baseline.

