Individuals who remain eligible for the study following clinical intake assessments, research intake assessments, review of medical record and assessment for contraindications to MRI will be invited to participate. Once the participants complete all pre-treatment study procedures, all participant data will fall under intention-to-treat analysis, where dropouts and non-compliant participants may be followed up on with post-treatment assessments and follow-up assessments as with all other

participants. Veterans who are found to not meet inclusion criteria following pre-treatment assessment may be unenrolled from the study at the discretion of study staff. All Veterans who are removed from the study will be paid for all study procedures completed to that point.

Veterans who may be eligible for Neuroscience of Social Behavior (PC-0002) study will be asked to complete a Release of Information form to share their contact information with PC-0002 study staff. A copy of relevant de-identified assessment data (see attached list) may also be released to the PC-0002 staff once written informed consent has been obtained by them from the Veteran.

The research staff will explain the study to the veteran and will answer any questions he/she may have prior to obtaining written informed consent.

Veterans will be assured that their choice to participate, or not, will have no effect on their treatment, clinical care or relationship with their clinician.

II. Assessment and Intervention

Initial Visit: Consent and Pretreatment Procedures

After written informed consent has been obtained, participants will begin study procedures.

Participants will complete pretreatment interviews, including the CAPS-5, SCID-5-RV with a trained clinical interviewer prior to beginning treatment.

Participants will complete the study questionnaires on paper during the first week at FBRI and/or at the Salem VA Medical Center (questionnaire battery including, for example, PCL, SAS-SR, AQ, ITS, etc.). Additionally, acceptability of treatment will be assessed through measures of treatment credibility and satisfaction after three weeks of treatment and the end of treatment, respectively.

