Our goal is to have 44 subjects in each of the two treatment groups complete this study over the course of four years. From our past experience conducting studies of this complexity with specific inclusion/exclusion criteria, we anticipate needing to enroll 1.5 subjects to achieve 1 subject who meets criteria and finishes the study. Thus, we multiplied our target of 88 subjects by 1.5 to reach our total sample size of **132**.

PROVISIONS FOR MANAGING & REPORTING ADVERSE EVENTS:

During all phases of the study, a doctorate-level clinician will be available for consultation and to help manage any negative reactions that occur in response to the neuroimaging sessions. All study staff working with the patients will be trained in suicide risk assessment, basic suicidal crisis intervention skills, and the study's safety protocol.

If patients exhibit symptoms of significant distress or anxiety at any time during their participation in study procedures at FBRI, they will be guided through clinical techniques to help them regulate their distress. Their session may be terminated if deemed appropriate. If it is determined that they are expressing suicidal/homicidal ideation or thoughts of self-harm or harm to others, clinically

trained staff will work with the veteran to reduce distress and/or acute suicide or homicide risk. When the veteran feels calm and is determined by staff to not be an imminent risk to self or others, they will be escorted back to the residential unit by a trained research staff member via the VA vehicle. If a veteran has driven or ridden in a private vehicle to the appointment and the veteran is deemed stable and safe by staff, they may be allowed to drive their vehicle back to the Salem VA and check in to the residential unit. If at any time clinical staff determine that the Veteran is an imminent risk to self or others and/or not safe to independently drive or ride in a private vehicle, the Veteran will be transported via the VA vehicle or ambulance, whichever is clinically indicated. Study personnel will remain with patients determined to be an imminent risk to self or others until direct hand off to a VA clinician or EMS response is possible.

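### The SAP compares arms on pre-to-post change and does not adjust for the baseline value of each outcome: a valid test under randomisation, but usually a less precise one whose estimate moves with any baseline gap

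*SAP*

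**What the plan says.** The SAP is a single paragraph. It describes a regression approach applied "on both primary (CAPS-5 and SAS-SR) and secondary (PCL-5, AQ, ITS) outcome measures", with two time points, before and after treatment. The test is named: "The Time x Treatment interaction was be used to test whether TMT improves outcomes relative to EXP+EDU". The only covariate is explained this way: "age was entered as a co-variate as the two treatment arms differed in age at baseline". It describes no random effect, covariance structure or constraint on the baseline means. It does not say whether age enters as a main effect only or also interacts with time.

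The protocol has no statistical analysis section that would fill these gaps. It does show that baseline values are collected. Under Assessment and Intervention, Initial Visit, it says: "Participants will complete pretreatment interviews, including the CAPS-5, SCID-5-RV with a trained clinical interviewer prior to beginning treatment". The same section places the questionnaire battery, with PCL, SAS-SR, AQ and ITS among its examples, in the first week.

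Two design facts bear on the point. Under Sample Size: "Our goal is to have 44 subjects in each of the two treatment groups complete this study over the course of four years". Under Study Design, the residential unit offers one arm at a time and the order of offering is randomised, so a veteran's arm depends on when he or she is on the unit.

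**The concern.** In a two-time-point model the pre-treatment score is part of the response. The interaction therefore uses it by subtraction, which fixes the slope of post on pre at 1. Where the true slope differs from 1, subtraction has two costs. It leaves in variance that the baseline score could have explained. It also lets a baseline difference between arms carry into the estimate: if the slope is below 1, the arm that starts worse tends to show more improvement whatever its treatment.

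Both costs matter in a trial that aims for 44 completers per arm, states no power calculation, and reports that its arms already differed on one baseline variable. Both primary outcomes are affected.

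**Working it through.** **The plan's own figure.** The only design figure is enrolment: 2 x 44 = 88 completers, and 88 x 1.5 = 132, as stated. There is no power figure to reproduce.

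**Inputs.** From the documents: two time points, age as the only named covariate, and 44 per arm. Not given, so assumed and shown over a range: the pre/post correlation r, the ratio k = SD_post/SD_pre, a difference of 0.5 SD, and a two-sided 5% level.

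**Step 1: what is tested.** With complete pairs, the Time x Treatment coefficient is (mean post - mean pre) in one arm minus the same quantity in the other. In simulated trials with age as a main effect, the coefficient equalled the raw difference in mean change to within 2e-15. So age entered only as a main effect does not alter the tested contrast. If age also interacts with time, the contrast is adjusted for age but still not for the baseline outcome.

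**Step 2: variance per subject.**
- Change: SD_pre^2 + SD_post^2 - 2r x SD_pre x SD_post
- Baseline-adjusted: SD_post^2 x (1 - r^2)
- Difference: (SD_pre - r x SD_post)^2

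The difference is never negative. It is zero when r x k = 1.

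**Step 3: variance ratio, adjusted divided by change.** With k = 1 it reduces to (1 - r^2)/(2(1 - r)) = (1 + r)/2. With k = 1.2 it is 1.44(1 - r^2)/(2.44 - 2.4r).

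| r | k = 1 | k = 1.2 |
|---|---|---|
| 0.3 | 0.65 | 1.3104/1.72 = 0.76 |
| 0.5 | 0.75 | 1.08/1.24 = 0.87 |
| 0.7 | 0.85 | 0.7344/0.76 = 0.97 |

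At r = 0.7 and k = 1.43 the slope is 0.7 x 1.43 = 1, both variances are 1.04 SD_pre^2, and nothing is gained. In simulation with k = 1 (4,000 trials per r), the inverse ratio, change over adjusted, was 1.59, 1.33 and 1.17, against 1.54, 1.33 and 1.18 from theory.

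**Step 4: what that means at 44 per arm, k = 1.** Dividing 44 by the ratio, the adjusted analysis works like a change-score analysis with about 68, 59 and 52 per arm. Power for an assumed 0.5 SD difference uses the t formula with SD sqrt(2(1 - r)) for change and sqrt(1 - r^2) for adjusted:

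| r | Change | Adjusted |
|---|---|---|
| 0.3 | 50% | 68% |
| 0.5 | 64% | 76% |
| 0.7 | 85% | 90% |

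A normal approximation gives values within about one point. These figures are illustrative: they assume equal SDs and independent veterans, and they ignore clustering by offering period.

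**Step 5: shift with a baseline gap.** Given a baseline gap g between arms, the change estimate moves by (r x k - 1) x g. With k = 1 that is -(1 - r) x g. A gap of one standard error at 44 per arm is sqrt(2/44) = 0.21 SD, which moves the estimate by about 0.15, 0.11 and 0.06 SD at r = 0.3, 0.5 and 0.7. In simulation the change estimate moved by -0.74, -0.51 and -0.31 per unit of gap, and the adjusted estimate by -0.04, -0.01 and -0.01.

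**The case against.** The strongest reply is that this is a choice about efficiency and that the planned test is not invalid. That stands. Under randomisation the change-score contrast is unbiased on average and keeps its type I error. A reader might infer that regression to the mean has been counted as a treatment effect in this trial. The documents do not show that: the only baseline difference they report is in age, and none is reported for CAPS-5 or SAS-SR.

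A reader might also infer that adjustment gains precision whenever r is below 1. That holds only when the SDs are equal; in general the gain disappears when r x SD_post/SD_pre = 1. Unequal SDs are plausible here, because entry requires current PTSD on the CAPS-5, which truncates the baseline score but not the post score. Truncation can also lower r, which pushes the other way, so the net size is unknown.

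Third, baseline gaps may not be chance. Arms followed the unit's offering period, and the protocol applies its exclusion criteria during analysis. If gaps reflect differences between cohorts, the two methods can target different quantities, and adjustment is not guaranteed to be less biased. This stands, and it is a reason to show both results.

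Fourth, the SAP says only that a regression was used, and a repeated-measures model with a common baseline mean would also test a Time x Treatment term. That is possible, but no such constraint is described, and the plain reading is an unconstrained interaction.

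Fifth, the SAP is dated June 2023 and reports the analysis largely in the past tense, so replacing the primary test now would be a post hoc switch. This stands and shapes the remedy.

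**Conclusion.** The point holds as a matter of precision and of sensitivity to observed baseline gaps. With complete pairs and no baseline constraint, the SAP tests the difference in mean change. In large samples this is never more precise than baseline adjustment (which costs one degree of freedom) and is equally precise only when the post-on-pre slope is 1.

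The size depends on quantities the documents omit. Over r = 0.3 to 0.7, adjustment would cut the variance by 35% to 15% with equal SDs. At an SD ratio of 1.2 the cut is 13% at r = 0.5 and 3% at r = 0.7. With equal SDs the loss is also small above about r = 0.8, where the ratio is 0.90.

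The documents do not support saying that the planned test is biased, that its error rate is inflated, or that the power figures above are this trial's actual power. Nor does the point extend to the brain measures: the SAP paragraph covers clinical outcomes only, and the protocol frames its mediation hypotheses in terms of pre/post changes.

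**What to change.** For each of the five clinical outcomes, estimate the treatment effect by regressing the post-treatment score on treatment, the pre-treatment value of the same outcome and age. Alternatively, use a repeated-measures model with a common baseline mean, which also keeps veterans who have only a baseline; that fits the protocol's statement that everyone who completes the pre-treatment procedures falls under intention-to-treat. Give a 95% CI and report the result beside the Time x Treatment result.

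Because the SAP describes the analysis as done, enter this as a dated change, say that it was made after the reported analysis, and show both results whichever way they fall. State whether age interacts with time in the existing model. State also that, because arms were assigned by offering period, baseline adjustment does not guarantee removal of bias from baseline differences that are not due to chance.

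The cost is a short SAP addition, a re-run on data already held, and a disclosed post hoc change. No new data are needed.
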